Hemodialysis Access Surveillance Evaluation (HASE) Study

Protocol Title:

Transonic Hemodialysis Access Surveillance Evaluation (HASE) Study

Objectives

The National Kidney Foundation Kidney Disease Outcomes Quality Initiative (KDOQI) recommends an organized monitoring/surveillance approach with regular assessment of clinical parameters of the arteriovenous access and hemodialysis (HD) adequacy. Data from the clinical assessment and HD adequacy measurements should be collected and maintained for each patient's access and made available to all staff. The data should be tabulated and tracked within each HD center as part of a Quality Assurance (QA)/continuous quality improvement (CQI) program (1).

The evidence from observational studies has emphasized that implementation of a surveillance program is beneficial in regard to access thrombosis, hospitalization and cost burden (see below). However, small sample sizes, randomized studies with suboptimal design and power to detect the difference have questioned the validity of the available information. National debates are beginning to express the futility of the surveillance approach. A well-designed randomized controlled trial that is adequately powered to evaluate multiple variables such as access thrombosis, cumulative access patency, need for tunneled hemodialysis catheters and hospitalizations (all of these parameters can easily be extrapolated to cost) is desperately needed.

Background

Hemodialysis vascular access dysfunction contributes directly to morbidity and mortality and adds to the cost of medical care of dialysis patients (1, 2). While access dysfunction presents several predicaments (prolonged bleeding, edema, high recirculation, low dialysis adequacy or frequently alarming dialysis machine) access thrombosis is the most feared complication. In order to provide an uninterrupted, life-saving dialysis therapy, a clotted access requires an urgent intervention (either thrombectomy or insertion of a tunneled dialysis catheter). Additionally, even after a successful thrombectomy procedure, a thrombotic episode in and of itself can affect the longevity of the access even after a successful thrombectomy procedure.

Vascular access stenosis develops as a result of neointimal hyperplasia and is observed in almost all of the patients with a clotted arteriovenous access (3, 5). It is also the most common cause of hemodialysis vascular access dysfunction. Indeed, a great majority of hemodialysis patients with an arteriovenous access will develop vascular stenosis (4).

While reduction in the blood flow and its subsequent recirculation is relatively a common cause of low Kt/V, the presence of stenosis is the most common cause of reduced blood flow rates. Data have indicated that for every 0.1 decline in Kt/V there is a significant increase in hospitalizations, hospital days and Medicare cost (5). In this context, the detection of the presence of vascular stenosis and its prompt treatment with percutaneous transluminal angioplasty (PTA) is of paramount importance for hemodialysis patients receiving treatment with hemodialysis. Several centers across the United States are

Hemodialysis Access Surveillance Evaluation (HASE) Study

performing PTA successfully on an outpatient basis (6). There is evidence that treatment of vascular access stenosis might decrease vascular access thrombosis (7-9).

There are a number of techniques that have been used to measure intra-access blood flow. However, most of these techniques have significant limitations. An ideal surveillance method is the one that can be performed during hemodialysis treatment such as ultrasound dilution technique (UDT) (Transonic) to enable regular periodic measurements and more compliance from patients (no additional appointments are required).

The National Kidney Foundation Kidney Disease Outcomes Quality Initiative (KDOQI) recommends that access blood flow with ultrasound dilution be performed monthly during the first 1.5 hour of the treatment to eliminate error caused by decrease in cardiac output or blood pressure related to ultrafiltration or hypotension (1). The official KDOQI recommendation indicates that an access flow of less than 600 ml/minute in arteriovenous graft and less than 500 ml / minute in arteriovenous fistula or if the access flow is 1000 ml/minute that has decreased by more than 25% over 4 months, the patient should be referred for hemodialysis access angiogram for further evaluation for the presence of stenotic lesions (1) (Table 1).

Table 1. Indications for referral for arteriovenous access angiogram Based on access blood flow measurement as set by KDOQI guidelines (1)	
Arteriovenous Fistula (AVF)	Arteriovenous Graft (AVG)
access flow rate less than 500 mL/min	access flow rate less than 600 mL/min in grafts
	If access flow is 1000ml/min that has dropped 25% over 4 months
Prospective trend analysis of the test parameter has greater power to detect dysfunction than isolated values alone	
Persistent abnormalities in any of the monitoring or surveillance parameters should prompt referral for access angiogram	

A number of observational studies have found a substantial decrease in the graft thrombosis after implementing a surveillance program (12–16). Based on these data the KDOQI vascular access guidelines have emphasized that hemodialysis units should implement graft surveillance programs and refer patients with suspected graft stenosis for preemptive angioplasty (1). Although there is a paucity of randomized control studies to evaluate hemodialysis access surveillance, the existing controlled trials have raised serious doubts regarding the validity of this approach (17 –25). Serious concerns are expressed regarding surveillance and national debates are beginning to express the futility of this approach. A careful analysis, however, of the available randomized trials points out significant limitations of these studies. Table 2 provides a summary of these trials (11). A brief synopsis of these studies is provided below.

Hemodialysis Access Surveillance Evaluation (HASE) Study

Table 2. Randomized clinical trials comparing surveillance to monitoring					
Study	Number of patients	Surveillance method	Type of access	Primary outcome	Surveillance (Beneficial or not beneficial)
Sands et al 1999 (23)	103	
 • Access flow • Static venous pressure 	68 AVF 35 AVG	AV access thrombosis	Beneficial
Moist et al 2003 (19)	112	
 • Access flow • Dynamic venous pressure 	AVG	AV access thrombosis or loss	Not beneficial
Ram et al 2003 (17)	101	
 • Access flow • stenosis 	AVG	AV access thrombosis or access survival	Not beneficial
Polkinghorne et al 2006 (24)	137	
 • Access flow 	AVF	Significant stenosis	Not beneficial
Mayer et al 1993 (25)	70	
 • Duplex Scan (Ultrasound) 	AVG	AVG Survival	Beneficial
Malik et al 2005 (21)	192	
 • Duplex Scan (Ultrasound) 	AVG	AVG Patency	Beneficial
Robbin et al 2006 (18)	126	
 • Duplex Scan (Ultrasound) 	AVG	AVG Survival	Not beneficial
Tessitore et al. 2004	79	
 • Access flow 	AVF	Thrombosis	Beneficial

Study Design

Randomized, Prospective Clinical Trial. Patients, PI, funder (Transonic) and statistician blinded (this will be implemented in Velos). Intervention and standard of care are different and cannot be blinded from attending nurses or clinic personnel. If a patient needs to switch schedules, they need to switch to shift that matches their protocol. Otherwise, they will need to switch protocols. No Transonic (funding) personnel will be involved in study design, protocol, analysis, or publication.

Randomization:

Patient is consented, baseline assessment taken, and evaluated for inclusion before randomization (baseline data will be included in analysis to determine representativeness of study patients to clinic patients). Randomization will occur after enrollment period ends.

The intervention and control protocols are significantly different that individual patients in the same dialysis session would be able to identify which arm they are in. Therefore, blocks of patients will be randomized according to dialysis schedule within each clinic.

Hemodialysis Access Surveillance Evaluation (HASE) Study

Because the staffing is similar across shifts, we will do block randomization where all patients in a shift are assigned to the same protocol at each clinic site. For each clinic, the blocks will be given a number based on chronological order (Monday 1st shift = 1, Monday 2nd shift = 2 +, Monday 3rd shift = 3, Tuesday 1st shift = 4, Tuesday 2nd shift = 5, Tuesday 3rd shift = 6). For each clinic site, a coin will be flipped in front of two witnesses: heads = first group treatment; tails = first group control. Then a die will be rolled. The number that is rolled will the first group assigned (based on coin toss). The remaining groups will be allocated in sequence. For instance, if the coin lands on heads and the die lands on 3, Monday 3rd shift is intervention, Tuesday 1st shift is control, Tuesday 2nd shift is intervention, Tuesday 3rd shift if control, Monday 1st shift is intervention and Monday 2nd shift is control. If a patient has to switch dialysis schedules, care must be taken to place them in the same arm.

Inclusion and Exclusion Criteria

Inclusion criteria:

Chronic hemodialysis patients undergoing dialysis therapy via an upper extremity arteriovenous access (arteriovenous fistula or an arteriovenous graft) will be enrolled to have monthly surveillance flow measurement using Transonic system or physical examination of the arteriovenous access by qualified person at least once a month for a period of 2 years.

Exclusion criteria:

- Patients requiring surgical intervention on the arteriovenous access.
- History of access thrombosis (one or more access thrombosis of the current AV access).
- Patients with signs of access infection.
- Patients with a malignancy.
- Patients with life expectancy of less than six months.
- Unable to understand the study.
- Unable to sign the consent form.
- Patients with psychiatric disorder.
- Age less than 18 or greater than 80 years.
- Adults unable to consent
- Individuals who are not yet adults (infants, children, teenagers)
- Pregnant women
- Prisoners

Procedures Involved

Chronic hemodialysis patients receiving treatment with an upper extremity arteriovenous access will be enrolled in this 2 year study. End of study starts as last patient from 450 completes follow-up. Patients would be randomly assigned into surveillance or the control group. Randomization will take a cluster pattern per shift. (shift randomization).

Hemodialysis Access Surveillance Evaluation (HASE) Study

Surveillance group

- a. Surveillance group would receive monthly blood flow surveillance by ultrasound dilution technique (using the Transonic system) plus standard care (see below). Patients would be referred for an intervention based on the current KDOQI recommendations i.e. access flow of less than 600 ml/minute for arteriovenous grafts and less than 500 ml/minute for patients with arteriovenous fistulas or if the access flow is 1000 ml/minute that has decreased by more than 25% over 4 months (1). In addition to the detection of access dysfunction, the time interval between the detection of access dysfunction by the Transonic system and the intervention will also be recorded.
- b. Patients will be referred for an intervention if clinical indication is met. Clinical indications include prolonged bleeding for more than 30 minutes (cannot be explained by medication), upper extremity edema, difficult cannulation, aspiration of clots during cannulation, aneurysmal formation. Access pressure that prevents normal HD machine operation (such as high venous pressure [>250 mm Hg] on three or more consecutive dialysis treatments, negative arterial pressure [<-250 mm hg] on three or more consecutive dialysis treatments). Any Kt/V that cannot be explained by other factors and high recirculation rate of more than 10% would be checked by Transonic Recirculation/flow test prior to referral (rear event).

Control group

Control group will receive standard monitoring (standard care). Standard monitoring is physical examination by a qualified individual (nurse) at each dialysis encounter. Patients will be referred for an intervention if clinical indication is met. Clinical indications include prolonged bleeding for more than 30 minutes, low Kt/v that cannot be explained by other factors, high venous pressure (>250 mm hg) on three or more consecutive dialysis treatments, negative arterial pressure (<-250 mm hg) on three or more consecutive dialysis treatments, upper extremity edema, difficulty cannulation, aspiration of clots during cannulation, aneurysmal formation and high recirculation of more than 10%.

Enrollment period

Enrollment period is expected to be 3-6 months.

Transonic measurement protocol:

Access recirculation, access flow would be determined using the ultrasound dilution technique (Transonic system).

1. Within 90 min of the beginning of HD session HD03 sensors are clamped HD tubing lines
2. Recirculation, access flow will be performed according to HD03 Manual.
3. Post intervention evaluation is as per each arm follow up unless other follow up deemed necessary by the interventionalist.

Hemodialysis Access Surveillance Evaluation (HASE) Study

Data Management

Primary Hypothesis:

H_0 : Patients screened monthly with Transonic Ultrasound Dilution Technique (UDT) and followed up with proactive intervention (if clinically indicated) will not have a rate of access thrombosis that is different than patients receiving physical examination and reactive intervention (if clinically indicated).

Secondary Hypotheses:

H_{0-1} : Patients screened monthly with UDT and followed up with proactive intervention (if clinically indicated) will not have a time to thrombosis that is different than patients receiving physical examination and reactive intervention (if clinically indicated)

H_{0-2} : Patients screened monthly with UDT and followed up with proactive intervention (if clinically indicated) will not have a number of angioplasty procedures that is different than patients receiving physical examination and reactive intervention (if clinically indicated)

H_{0-3} : Patients screened monthly with UDT and followed up with proactive intervention (if clinically indicated) will not have a number of thrombectomy procedures that is different than patients receiving physical examination and reactive intervention (if clinically indicated)

H_{0-4} : Patients screened monthly with UDT and followed up with proactive intervention (if clinically indicated) will not have a rate of tunneled dialysis catheter (TDC) that is different than patients receiving physical examination and reactive intervention (if clinically indicated)

H_{0-5} : Patients screened monthly with UDT and followed up with proactive intervention (if clinically indicated) will not have a rate of non-tunneled dialysis catheter (non-TDC) that is different than patients receiving physical examination and reactive intervention (if clinically indicated)

Sample Size:

$\alpha = 0.05$, $\beta = 0.80$, 2-sided (testing benefit and harm)

Main predictor: Treatment or control; Main outcome: Thrombosis or no—two-sided therefore chi-square for proportions of dichotomous variables was used for sample size calculations.

Treatment versus control estimates of thrombosis (based on Tessitore 2004; Scaffaro 2009, Moist 2003, Robbin 2006, Sands 1999, Ram 2003, Tessitore 2008): 34% in control; 24% in treatment (effect size 30%); 342 per group; loss to f/u (move, transplant, different clinic) 5% = $1/(1-.5)=1.05=359$ (low estimate); loss to mortality 10% a year = 1.11 2x (per [name]) = 443

Variables to be collected at baseline:

age, sex, race (white, black, Asian/Pacific Islander, American Indian/Alaskan Native), ethnicity (Hispanic or not), insurance type (private, Medicaid, Medicare,

Hemodialysis Access Surveillance Evaluation (HASE) Study

Veterans/Military, uninsured), length of time in dialysis (weeks); diabetic (y/d), CAD, PVD, HTN, how long access has been in place (weeks), location (Right/Left, arm/forearm), type of access (AVF or AVG), other clinical variables, button hole, history previous access (Y/N), history of previous catheter (Y/N), length of catheter placement/use (Days)

Variables to be collected monthly:

Monthly questionnaire.

Statistical Analysis:

- **Step 1:** Descriptive analysis to assess similarity of patients between trial arms and to assess representativeness of study participants to hemodialysis patients (generalizability).
- **Step 2:** Descriptive analysis for primary outcome (chi-square) and secondary outcomes (t-test or non-parametric equivalent)
- **Step 3:** Kaplan-Meier Survival Curve (unadjusted)
- **Step 4:** Survival Time Analysis Cox proportional hazards model (adjusted)
- **Step 5:** Multilevel regression with random effects in a mixed regression model to adjust for potential group-level RN, center, city effects. Primary analysis is a dichotomous variable (y/n). Secondary analysis outcomes continuous but may be treated as categorical variables

Covariates for evaluation in the models: individual-level predictors: age, race, sex, insurance, length of time in dialysis (weeks), diabetes (y/n), CVD (y/n), how long access has been in place (weeks), access location, type of access, location of access , length of time in study before thrombosis or mortality (weeks); other significant clinical variables group-level predictors: RN, dialysis center, city

Cross-overs: intervention participants who do not get clinically indicated treatment will be analyzed in two ways--included in treatment arm (intention-to-treat) and excluded (per protocol)

Statistical monitoring: analysis will be conducted 6 months; 12 months; 18 months; and 24 months. If a clear benefit is identified early or if the intervention is unexpectedly harmful, the study will be stopped early.

Risks to Subjects

Risk from Ultrasound Dilution Technique: UDT is a non-invasive procedure that generates no risk to patients undergoing hemodialysis. We do not anticipate any problems as a result of patients undergoing this procedure.

Risk to Privacy: There may be breach of confidentiality regarding protected health information. To minimize the potential risk to privacy all data are de-identified with use of study specific ID numbers only. To ensure that participants' confidentiality is

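### Whole shifts are randomised within clinics, but the sample size has no design effect and no planned analysis contains shift

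*Combined protocol and SAP*

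**What the plan says.** **Allocation.** The Randomization section states "we will do block randomization where all patients in a shift are assigned to the same protocol at each clinic site". It introduces this with the remark "Because the staffing is similar across shifts". A coin and a die fix the arm of the first shift in each clinic, and then "The remaining groups will be allocated in sequence", alternating between arms. Procedures Involved also describes the scheme as cluster randomisation by shift. Study Design adds a rule for patients who move: "If a patient needs to switch schedules, they need to switch to shift that matches their protocol. Otherwise, they will need to switch protocols".

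**Sample size.** The Sample Size section says that "chi-square for proportions of dichotomous variables was used for sample size calculations", with inputs "34% in control; 24% in treatment (effect size 30%); 342 per group". It then inflates for loss to follow-up and for mortality, reaching 443. It gives no intraclass correlation (ICC), shift size or design effect.

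**Analysis.** Step 2 is a chi-square for the primary outcome, labelled descriptive. Step 3 is an unadjusted Kaplan-Meier curve and Step 4 an adjusted Cox model. Step 5 is a mixed model with random effects, and it is where the primary analysis is mentioned. Its group-level terms are nurse, dialysis centre and city, and the covariate list repeats those three. Shift appears in none of the steps.

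**The concern.** The unit that was randomised should be visible to the analysis. Patients on one shift share a dialysis time, a room and probably some staff, and all receive the same protocol. If their thrombosis risks are positively correlated beyond what clinic explains, the arm comparison is less precise than a patient-level calculation assumes. Standard errors are then too small, the false-positive rate exceeds 5%, and the stated 80% power is too high.

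The terms in Step 5 do not settle this. Centre and city sit above the shift, and every clinic contributes shifts to both arms, so those terms leave the correlation between patients on one shift in the arm contrast. Nurse would replace shift fully only if each shift had a single nurse who worked no other shift, and partly if nurses were nested in shifts. The plan states neither. Its remark that staffing is similar across shifts could mean the same nurses or only the same staffing levels.

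**Working it through.** **1. Reproduce the plan's figure.** Inputs from Sample Size: 34% v 24%, two-sided alpha 0.05, power 0.80 (printed as beta). With mean proportion 0.29:

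n = [1.960·√(2·0.29·0.71) + 0.842·√(0.34·0.66 + 0.24·0.76)]² / 0.10² = 322.0

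Continuity correction: (322.0/4)·[1 + √(1 + 4/(322.0·0.10))]² = 341.7, the stated 342.

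Attrition: 342 × 1.05 = 359, and 359 × 1.11 × 1.11 = 442.3 (stated 443). Patient-level inputs and attrition account for every step, so the implied design effect is exactly 1.

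**2. Add a design effect.** DE = 1 + (m − 1)·ICC, where m is enrolled patients per shift and ICC is the residual correlation between patients on one shift within a clinic. The available text gives neither. Assumed: m = 5 to 15, ICC = 0.01 to 0.05. Error of a test that ignores shift = 2·[1 − Φ(1.96/√DE)]. Power uses the uncorrected formula at n/DE.

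| m | ICC | DE | Error | Power at 342 per group | Power at 225 per group |
|---|---|---|---|---|---|
| – | 0 | 1.00 | 5.0% | 82% | 65% |
| 5 | 0.01 | 1.04 | 5.5% | 81% | 63% |
| 5 | 0.05 | 1.20 | 7.4% | 75% | 57% |
| 10 | 0.02 | 1.18 | 7.1% | 76% | 58% |
| 10 | 0.05 | 1.45 | 10.4% | 67% | 49% |
| 15 | 0.05 | 1.70 | 13.3% | 60% | 43% |

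With continuity correction, power at 342 falls from 80% to between 78% and 56%. The last column is there because the planned total is 450 (Procedures Involved: "End of study starts as last patient from 450 completes follow-up"; also Recruitment Methods and Number of Subjects), or 225 per group before losses.

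**3. What the alternation balances.** Numbering the shifts 1 to 6 as the protocol does, all 12 coin and die results give {1, 3, 5} against {2, 4, 6}. Each arm gets one first, one second and one third shift, so clinic and shift position largely cancel. Day schedule does not: one arm has two Monday shifts and one Tuesday shift, the other the reverse, which leaves (Monday − Tuesday)/3 in the contrast. Residual shift effects also remain.

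**4. Simulation near the planned size.** Event risk 29%, six equal shifts per clinic, 20,000 runs; 15 clinics with m = 5 (450 patients), 8 with m = 10 (480), 5 with m = 15 (450). Error of a clinic-stratified Mantel-Haenszel test without shift:

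| Residual ICC | m = 5 | m = 10 | m = 15 |
|---|---|---|---|
| 0.01 | 5.4% | 6.0% | 6.5% |
| 0.02 | 5.8% | 7.1% | 9.0% |
| 0.05 | 7.6% | 10.3% | 13.5% |

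Clinic-specific day variation alone, at ICC 0.05, gives 5.5% to 7.8%.

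**5. Step 5 as written.** Linear approximation with centre and nurse but no shift, no patient covariates, 5 patients per nurse assumed, ICC 0.01 to 0.05:

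- Same nurses on every shift: 5.4% to 13.6%.
- Nurses each on one shift, two or three per shift (m = 10 to 15): 5.3% to 10.4%.
- One nurse is the whole shift: about 5%.

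**The case against.** **The harm is assumed.** The documents do not show that the residual ICC reaches 0.05. At 0.01 the error is at most about 7%, and at the lowest setting 5.5%. This stands as a limit on the size of the problem. It does not rescue the plan's figures, which are right only if the residual correlation is zero.

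**Balanced clinics partly protect the plain chi-square.** Its variance inflation is roughly 1 − ICC(clinic) + (m − 1)·ICC(shift). With clinic ICC 0.05 and shift ICC 0.01, simulated error is only about 5% to 6%. That trims the low end. At shift ICC 0.05 the error is still 6.9% to 12.7%. Step 2 also calls this test descriptive, so its error rate may not be that of the primary test.

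**Step 5 already handles clustering.** In part, yes. Nurse is a plausible source of correlation, because standard monitoring is a nurse's examination. Whether nurse captures shift depends on rosters that the plan does not describe.

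**The remedy is not perfectly matched to the allocation.** Each clinic has only two possible allocations, so a shift random effect relies on its model rather than on independent randomisation of shifts. The simulated remedy was a shift-level test with clinic as stratum, not the mixed logistic model itself. Both points stand as cautions.

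**Shift may be recorded anyway.** The variable lists are open-ended and the monthly questionnaire is not reproduced. Recording the current shift is, however, not the same as retaining the shift as randomised.

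**Conclusion.** The concern holds. Shifts are the randomised unit, the sample size contains no allowance for this, and no analysis names shift. The stated 5% error and 80% power are therefore not supported for this design.

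How far they are off depends on assumptions. Over 5 to 15 patients per shift and a residual ICC of 0.01 to 0.05, the effect runs from slight (about half a percentage point of error and one or two points of power) to serious (about 13% error and 60% power at 342 evaluable per group).

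The gap between 450 in total and 443 per group is a separate problem. It alone lowers power to 65% before attrition, and it costs more than clustering does over most of the assumed range.

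**What to change.** - **Primary analysis.** Name the Step 5 mixed-effects logistic model as primary, with a random intercept for shift as randomised within clinic, clinic as stratum, and a small-sample degrees-of-freedom correction. Shift position and day schedule are optional covariates; day schedule is the one the alternation leaves unbalanced. Keep the Step 2 chi-square descriptive.
- **Time to thrombosis.** Use a shift frailty or a shift-clustered robust variance in the Cox model.
- **Data.** Carry shift as randomised into the analysis dataset, so that a patient who later changes shift stays in the original cluster.
- **Power.** Restate it for the number actually planned, giving the expected patients per shift and a design effect over a stated ICC range.

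**Cost.** SAP wording and one retained variable that is known at randomisation. This point by itself asks for no more enrolment and no change to care. Intervals widen and the stated power drops. In simulation, a shift-level test with clinic as stratum kept error at 4.6% to 5.4% under residual ICC 0.01 to 0.05. With position and day covariates, its power near the planned size was 62% to 56% (m = 5), 62% to 49% (m = 10) and 55% to 40% (m = 15). That version becomes conservative if most shift variation, at ICC 0.05, is clinic-specific time-of-day variation (1.6% to 3.0% error) or clinic-specific day variation (3.5% to 4.2%).

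### The coin-and-die rule gives only two mirror-image shift patterns per clinic and nothing balances them across clinics, so day schedule can line up with arm by chance

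*Combined protocol and SAP*

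**What the plan says.** Study Design, Randomization makes the dialysis shift within a clinic the unit of allocation. "For each clinic, the blocks will be given a number based on chronological order": Monday 1st, 2nd and 3rd shift are 1 to 3, and Tuesday 1st, 2nd and 3rd are 4 to 6.

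Each clinic is handled separately: "For each clinic site, a coin will be flipped in front of two witnesses", with "heads = first group treatment; tails = first group control". The die then picks the starting shift: "The number that is rolled will the first group assigned (based on coin toss). The remaining groups will be allocated in sequence". The worked example shows that in sequence means strict alternation, wrapping from shift 6 back to shift 1: "if the coin lands on heads and the die lands on 3, Monday 3rd shift is intervention, Tuesday 1st shift is control", and so on round the ring.

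On timing: "Randomization will occur after enrollment period ends".

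The only reason given for treating shifts as alike is that their staffing is similar. Under Statistical Analysis, the group-level predictors are nurse, dialysis centre and city. Neither shift nor day schedule is listed.

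**The concern.** A coin and a six-sided die appear to offer 12 different allocations. If they offer only two, each clinic's six shifts carry a single random bit, and the same three shifts always share an arm within a clinic.

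Clinics toss independently and no rule balances the patterns between them. Most or all clinics can therefore land on the same pattern. One arm would then hold two Monday shifts and one Tuesday shift at every clinic, always in the same day-by-shift combination. Similar staffing does not make the patients on different shifts alike. Any difference in thrombosis risk between those slots that the clinics share would enter the arm comparison, and a bad draw cannot be undone once follow-up has begun.

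**Working it through.** **Inputs.** Six ordered shifts, one coin and one die per clinic, and cyclic alternation (Study Design, Randomization). Planned risks 34% and 24%, a difference of 10 points (Sample Size). 450 patients (Number of Subjects). The number of clinics k is not in the text available: Recruitment Methods refers back to a list of centres that is not included. I therefore show a range.

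**1. Reproduce the worked example.** Heads and 3 give Mon 3rd surveillance, Tue 1st control, Tue 2nd surveillance, Tue 3rd control, Mon 1st surveillance, Mon 2nd control. This matches the protocol.

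**2. Enumerate.** Shift s takes the coin's arm when s minus the die number is even, and the other arm when it is odd. Six is even, so wrapping does not change this. Only the parity of the die matters, and changing parity has the same effect as turning the coin over. Of the 2 x 6 = 12 outcomes:
- 6 give surveillance = {Mon 1st, Mon 3rd, Tue 2nd};
- 6 give surveillance = {Mon 2nd, Tue 1st, Tue 3rd}.

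Each pattern has probability 1/2. Each gives both arms one 1st, one 2nd and one 3rd shift, with a 2:1 or 1:2 Monday/Tuesday split. The result needs an even number of shifts; the protocol defines six for each clinic.

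**3. Chance that clinics match.** P(all k alike) = 2 x (1/2)^k = 2^(1-k). Partial matching is commoner: with 4 clinics, a 4-0 or 3-1 split has probability (2 + 8)/16 = 62.5%.

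**4. Size of the shared-slot error.** Assume slot risks common to the clinics vary independently with SD 5 points. The documents give no figure for this. The difference between two means of three slots has SD sqrt(2/3) x 5 = 4.08 points when all clinics match (2.4 to 5.7 for an assumed SD of 3 to 7). Averaged over independent tosses it is 4.08/sqrt(k). With mirrored pairs and equal slot sizes it is 0 for even k and 4.08/k for odd k.

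| k | P(all match) | SD, independent tosses | SD, mirrored pairs |
|---|---|---|---|
| 2 | 50% | 2.9 | 0 |
| 3 | 25% | 2.4 | 1.4 |
| 4 | 12.5% | 2.0 | 0 |
| 5 | 6.25% | 1.8 | 0.8 |
| 6 | 3.1% | 1.7 | 0 |
| 8 | 0.8% | 1.4 | 0 |
| 10 | 0.2% | 1.3 | 0 |

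The size depends on what differs between slots. If only time of day matters, the error is 0. If only Monday/Tuesday matters (SD 5 for each day), the all-match contrast is one third of the difference between the two days: 5 x sqrt(2)/3 = 2.4 points.

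**5. What can be separated when all clinics match.** Code arm as +1/-1. Arm is balanced over shift number. Its mean is +1/3 on one day and -1/3 on the other, so R-squared on day and shift number is 1/9. The variance of the arm effect is multiplied by 1/(1 - 1/9) = 1.125, a rise of 12.5%. The model has 5 columns for 6 slots and full rank. Only a day-by-shift effect cannot be separated from arm.

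**6. Scale against sampling error.** With 225 per arm and a common risk of 29%, the sampling SD is sqrt(0.29 x 0.71 x 2/225) = 4.3 points. With 4 clinics, the slot error raises it to sqrt(4.28^2 + 2.04^2) = 4.7 on average, and to sqrt(4.28^2 + 4.08^2) = 5.9 if all match. In null simulations of this setting, a shift-level test rejected 11 to 12% of the time in all-match draws but near 5% over all draws.

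**The case against.** Much of the case on the other side stands.

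- **Bias.** A reader might infer that the rule is biased. It is not: every shift has a 1/2 chance of either arm, and a shift-level test keeps its level over repeated randomisation. The 11 to 12% figure is conditional on an unlucky draw.
- **Cause.** A reader might blame the two-pattern collapse for the average errors of 2.4, 2.0 and 1.8 points. A free choice of any 3 of the 6 shifts at each clinic (20 patterns) gives the same SDs. They come from tossing independently in few clinics. What the collapse adds is the all-match tail: 12.5% for 4 clinics, against 20^(1-4) = 0.0125% under free choice.
- **Separability.** A reader might infer that no analysis could separate arm from shift. Step 5 of the working shows that additive day and shift-number effects can be separated. The plan, however, lists neither term, and the Step 2 chi-square adjusts for nothing.
- **Planned adjustment.** The Cox and multilevel models include age, race, sex, insurance, time on dialysis, diabetes, cardiovascular disease, and access age, location and type. Measured differences between shifts can therefore be reduced. Unmeasured ones remain.
- **Number of clinics.** The all-match chance is below 1% from 8 clinics. The documents do not support a claim that matching is likely without knowing k.

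**Conclusion.** The structural finding is exact: two mirror-image patterns per clinic, a die with no effect, and nothing that balances patterns across clinics. The consequence is a chance imbalance in the one allocation realised. It is confined to the day schedule and the day-by-shift combination, because time of day is already balanced within each clinic when shifts are of equal size.

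The risk of complete alignment is substantial with 2 to 4 clinics (50% to 12.5%) and small with 8 or more. Under the assumed slot SD of 5 points, the shared error has SD 4.1 points if all clinics match and about 2 points on average for 3 to 5 clinics, against the planned 10. These sizes rest on that SD, on slot effects shared by the clinics, and on equal slot sizes.

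The documents do not support saying that the trial is biased, or that arm will be confounded with shift beyond repair. They do support a cheap change before randomisation.

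**What to change.** 1. Since allocation waits until enrolment has closed, randomise the clinics in pairs on one date, matched as closely as possible on shift sizes.
2. List the six patterns that give each arm one 1st, one 2nd and one 3rd shift with a 2:1 day split. There are 2^3 = 8 patterns with one of each shift number per arm, less the 2 that put all of one day in one arm. Roll the die once per pair to choose the first clinic's pattern, and give the second clinic the mirror image. An unpaired clinic draws alone.
3. Add day schedule and shift number as covariates in the adjusted models.

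For 4 clinics this gives 6^2 = 36 possible allocations, against 2^4 = 16 now. A simpler version keeps the present two patterns and reverses the coin at the second clinic of each pair. It removes the same shared-slot error but leaves only 2^2 = 4 allocations.

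**Cost.** One paragraph of protocol text, one line in the analysis section and three model degrees of freedom (one for day, two for shift number); no extra patients, visits or staff. Paired clinics must be randomised together. Balance is only approximate when shift sizes differ or the number of clinics is odd.
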